Cigarette smoking can impact metabolism of chemotherapy and targeted therapy, increase risk of radiation therapy complications, increase rates of postoperative complication and mortality, increase risk of recurrence, and decrease rates of survival. Despite these effects, 64% of cancer patients who smoke pre-diagnosis will continue to smoke post-diagnosis [1]. Providing smoking cessation programs to help cancer patients quit smoking meets an important healthcare need and fills a necessary gap in oncology treatment. National Comprehensive Cancer Network guidelines for treating smoking cessation provide no guidance for the tailoring of cessation interventions for cancer patients (NCCN.org). A major barrier to provide smoking cessation support to cancer patients are a lack of appropriate resources, lack of provider training and their time to offer cessation treatments [2]. To address these gaps and limitations, we developed the first smartphone app for smoking cessation specifically tailored to cancer patients. The app is called Quit2Heal.

Specific Aim. This pilot project provides a timely opportunity to pursue one key aim: conduct a pilot trial comparing the Quit2Heal application for cancer patient smokers to the NCI Smokefree.gov Quit Guide application for general population smokers.

Our primary aims are to: (1) assess the feasibility of the recruitment methods (e.g., cancer treatment center vs Facebook ads), (2) assess participants' engagement with and receptivity to the Quit2Heal app, (3) assess usability of the Quit2Heal app, and (4) show the Quit2Heal app's cessation progress and outcomes compared to NCI Quit Guide in short-term (2 month) follow-up.

RESEARCH STRATEGY

Research Plan and Methods for RCT

[figure not shown]
Timeline. Over the course of 18 months, we will recruit, enroll, and randomize participants, conduct a 2-month post-randomization survey data collection, data entry, and quality control, and analysis.

Table 1. Schedule of key activities.

Quai	rter	Spring	Summer	Fall	Winter	Spring	Summer	Fall
1.	Recruitment	Χ	X	X	Χ	X		
2.	Interventions	Χ	X	X	Χ	X		
3.	Outcome Surveys		X	X	X	X	X	
4.	Data Entry & QC			X	X	X	X	X
5.	Analysis						X	X

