Randomized trial experimental design. We will conduct a two-arm randomized controlled trial that compares application-based ACT to an application-based smoking cessation intervention following US Clinical Practice Guidelines (Smokefree.gov). To balance baseline variables between the two conditions, following enrollment we will randomize participants.

Figure 1. Experimental Design

APPROACH

We will conduct a randomized effectiveness trial comparing our ACT smoking cessation application Quit2Heal to the NCI's Quit Guide application. Specifics on our pilot trial, research team, and research strategy are the following:

Eligibility Criteria: (1) age 18 or older, (2) diagnosed with cancer in the past 12 months, or currently receiving or planning in the next 3 months to receive cancer treatment, (3) has smoked a cigarette (even a puff) in the past 30 days, (4) interested in learning skills to quit smoking, (5) willing to be randomly assigned to either smartphone application, (6) resides in US, (7) has at least daily access to their own smartphone, (8) knows how to login and download a smartphone application from the Apple app store or Android Play app store, (9) willing and able to read in English, (10) not currently using cessation medications or enrolled in other smoking cessation programs, and (11) has never used the NCI's Quit Guide smartphone application. To increase follow-up retention, eligiblity criteria also include: (12) willing to complete one follow-up survey, (13) provide email, phone, and mailing address. Participants not eligible for or interested in randomization will be given the given the smokefree.gov website, the [name] phone number to reach their state's quitline, and the NCI's Quit Guide smartphone application.

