releases, and flyers with links to our recruitment website. Depending on the recruitment venue, relevant portions of our media kit will be distributed to Internet media (e.g., online sites and blogs), newspapers, radio stations, television stations, hospitals and community clinics, trade groups, quitlines, cessation websites, and Facebook Ads. We will also recruit through the National Cancer Institute Contact Center (NCICC, also known as NCI's Cancer Information Service), Memorial Sloan Kettering (MSK), and the Seattle Cancer Care Alliance (SCCA) and SCCA affiliate network sites. At NCICC, the trained information specialists will describe the study to potential participants (who call and disclose that they are cancer patients who smoke and would like to guit), using our call script, and will direct them to the recruitment website if they are interested in participating. At MSK and the SCCA clinic and affiliate network sites, fliers, brochures, and TV screen ticker-tape messages can be used to advertise the study, and site research personnel and/or healthcare providers can describe it to eligible participants. Additionally, [name] who runs the cessation program at SCCA SLU will offer the study as an option to eligible patients who have declined participating in her cessation program. [name] and other MSK or SCCA or affiliate network staff will only describe the study and direct patients to the study recruitment website; they will not be involved in the study consent or intervention, which will all take place on the study website and app. We expect to recruit approximately 25% of participants through the NCICC, MSK, SCCA sites and SCCA affiliate network sites.

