Usability of the Quit2Heal app. We will compare the two arms on items measuring the usability of the assigned program using descriptives. If participants indicate that they are willing to discuss their experience in the study, we will contact them to inquire about their user experience with the app. Responses will be used to qualitatively assess ease of use, appeal of the app design, and suggestions users may have for improvements.

Cessation outcomes and cessation progress at 2-month follow-up. We will report the 30-day point prevalence quit rate at 2-months post randomization, as well as secondary cessation outcomes 7-day and 24-hour point prevalence abstinence. We will provide both complete case and missing=smoking results for each study arm. Quit2Heal vs. NCI Quit Guide cessation rates will be compared using logistic regression, adjusting for the three factors used in stratified randomization: Heaviness of Smoking Index, Commitment to Quitting Smoking Score, and recruitment method.

Cessation progress outcomes will include number of 24-hour quit attempts, change in number of cigarettes smoked per day since randomization, nicotine dependence level, acceptance of cravings to smoke, commitment to quitting, and use of nicotine replacement therapy or medications to aid quitting. Tables with N (%) or mean (SD) by treatment arm and p-values obtained from logistic regression, linear regression, or negative binomial regression models adjusted for randomization factors will be provided.

PROTECTION OF HUMAN SUBJECTS

Risks to the Subjects

Human subjects' involvement and characteristics. We will conduct a two-arm randomized controlled trial that compares the Quit2Heal cancer-patient specialized application-based ACT to an application-based smoking cessation intervention following US Clinical Practice Guidelines (Smokefree.gov). To balance baseline variables

between the two conditions, following enrollment we will randomize with stratification according to these known predictors of smoking cessation: nicotine dependence (Heaviness Smoking Index cut off score of 4 [9]), motivation to quit (Commitment to Quitting Scale cutoff score of 4 [10], and recruitment method (clinic vs. social media). The hypothesized moderators will be measured at baseline. The hypothesized mediators will be assessed at both baseline and two months post randomization, while cessation and progress outcomes will be measured at 2 months post randomization.

Potential Risks

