treatment groups will be given information on pharmacotherapy for smoking cessation (e.g., nicotine patch) and how to obtain these medications.

Reporting Breaches and Complaints. Taken together, these measures will minimize risks to study participants. However, should a breach/complaint occur, or if a participant is not pleased with any of the surveys, or with the study's procedures, the study's scientific staff will attempt to address the concerns; if unsuccessful, the breach/complaint will be reported to the IRB office, and the participant will be referred to [name], Fred Hutch IRO Director.

Potential Benefits of the Proposed Research to the Subjects and Others.

Successfully assisting cancer patients who smoke to quit would have significant positive benefits to their health. Overall, participants assigned to either of the two interventions have the potential to benefit by quitting smoking and the potential short- and long-term health benefits of quitting on their cancer treatment and prognosis, and overall lifetime health.

Importance of Knowledge to Be Gained. The proposed intervention shows exciting promise for improving cessation rates among cancer patients, who currently do not have standard cessation interventions as part of their treatment. If effective, the public health impact of this low-cost intervention is significant. Even if the intervention is not better than our standard care control, it suggests the new intervention should be disseminated as a reasonable alternative to other publicly available application-based interventions.

INCLUSION OF WOMEN AND MINORITIES

The population for this study will be 60 adult male and female cancer patients who currently smoke and want to quit, or have quit smoking within in the past 30 days. Recruitment and eligibility screening methods are designed to achieve a broad representation of adult smokers that is 50% female and 25% minority race/ethnicity. The expected gender and race/ethnic distribution of the trial participants is reported in the Targeted/Planned Enrollment Table.

TARGETED/PLANNED ENROLLMENT TABLE

Total Planned Enrollment:

60

TARGETED/PLANNED ENROLLMENT: Number of Subjects					
Ethnic Category	Sex/Gender ¹				
	Females	Males	Total		
Hispanic or Latino	2	2	4		
Not Hispanic or Latino	43	13	56		
Ethnic Category: Total of All Subjects *	45	15	60		

Racial Categories			
American Indian/Alaska Native	1	0	1
Asian	0	1	1
Native Hawaiian or Other Pacific Islander	0	0	0

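### Should quit rates be split by smoking status at entry, because people who stopped in the past 30 days are eligible?

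*Combined protocol and SAP*

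**What the plan says.** Eligibility (Approach, Eligibility Criteria) turns on whether the person "has smoked a cigarette (even a puff) in the past 30 days"; smoking on the day of randomization is not required. The section on inclusion of women and minorities makes the consequence explicit: the population is "60 adult male and female cancer patients who currently smoke and want to quit, or have quit smoking within in the past 30 days".

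The fourth aim is to "show the Quit2Heal app's cessation progress and outcomes compared to NCI Quit Guide". Under the cessation outcomes heading, the plan says "We will report the 30-day point prevalence quit rate at 2-months post randomization", with 7-day and 24-hour abstinence as secondary outcomes. Results are given by arm, both for complete cases and with missing counted as smoking. The logistic model adjusts for the Heaviness of Smoking Index, the commitment score and recruitment method, which are also the stratification factors. Smoking status at entry is not named as a covariate, subgroup or table row.

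On progress, the plan says "Cessation progress outcomes will include number of 24-hour quit attempts, change in number of cigarettes smoked per day since randomization", followed by four further outcomes.

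The Analyses paragraph calls all the aims exploratory. Table 2 shows nine Tobacco Use items collected at baseline and at 2 months for Aim 4.

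**The concern.** A quit rate in a cessation trial is usually read as the proportion of smokers who stopped. Here a participant may already have stopped before randomization, and continued abstinence is scored the same as a new quit. If many such people enroll, part of the reported rate reflects relapse prevention, and a reader cannot tell how many people still smoking at entry gave up.

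A second worry runs the other way. Someone at zero cigarettes at baseline cannot show a fall in cigarettes per day and might report no new quit attempt. A good result could then look like no progress on those two outcomes.

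At stake is the meaning of the descriptive quit rates, which are a main product of a pilot of this size.

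**Working it through.** **What the documents give.** Planned N is 60. They give no expected quit rate, no share of recent quitters, no power calculation and no allocation ratio, so there is no figure of the plan's own to reproduce. All rates below are assumptions.

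**Clues to the share.** Criterion 4 asks that the person be "interested in learning skills to quit smoking", and criterion 10 that they be "not currently using cessation medications or enrolled in other smoking cessation programs". Both fit people still smoking better than people who have already stopped. The Recruitment text for the national contact center concerns people "who call and disclose that they are cancer patients who smoke". These clues suggest a small share but do not fix it.

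**Effect on the quit rate.** Let q be the share of recent quitters, m their abstinence at 2 months (assumed 0.40 to 0.80) and p the abstinence of those smoking at entry (assumed 0.10 to 0.20), with no loss to follow-up.

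- Overall rate: R = q·m + (1 − q)·p
- Rise over the smokers' rate: R − p = q·(m − p)
- Fraction of counted quits from recent quitters: q·m / R

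The low corner is m = 0.40, p = 0.20; the high corner is m = 0.80, p = 0.10.

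| q | People in 60 | Rise (points) | Fraction of quits |
|---|---|---|---|
| 2% | about 1 | 0.4 to 1.4 | 4% to 14% |
| 5% | 3 | 1.0 to 3.5 | 10% to 30% |
| 10% | 6 | 2.0 to 7.0 | 18% to 47% |

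Example at 5%: the rise is 0.05 × 0.20 = 0.010 to 0.05 × 0.70 = 0.035. The fraction is 0.02/0.21 = 0.095 to 0.04/0.135 = 0.296. In people, that is 3 × 0.40 = 1.2 to 3 × 0.80 = 2.4 quits.

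**Set against sampling error.** Assuming 30 per arm and a rate of 15%, the 95% half-width for one arm is 1.96 × √(0.15 × 0.85 / 30) = 0.128, or about 13 points. A rise of 0.4 to 3.5 points lies well inside that.

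**Effect on the arm comparison.** Entry status is fixed before randomization, so it can differ between arms only by chance. At q = 5% and 30 per arm, the chance imbalance (1.96 SD) is 1.96 × √(2 × 0.05 × 0.95 / 30) = 0.110. With p = 0.15 and m = 0.40 to 0.60, this moves the difference in quit rates by 0.110 × 0.25 = 0.028 to 0.110 × 0.45 = 0.050. The overall rates are then 0.1625 and 0.1725, so the half-width for the difference itself is 1.96 × √(2 × 0.1625 × 0.8375 / 30) = 0.187 to 1.96 × √(2 × 0.1725 × 0.8275 / 30) = 0.191. The imbalance is one component of that half-width; it does not add to it.

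**Partial cover in the model.** The Heaviness of Smoking Index is both stratified on and adjusted for. The title of its source in the reference list describes it as built on time to first cigarette and cigarettes per day, both close to current smoking. The documents do not show how it is scored for someone already abstinent, so the cover is partial at best.

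**What a smokers-only row would add.** At q = 5% it holds 57 people and 57 × 0.10 = 5.7 to 57 × 0.20 = 11.4 quits, about 6 to 11 across both arms before loss to follow-up. It would nearly repeat the overall row.

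**Progress outcomes.** Two of the six named outcomes could be affected, depending on item wording that is not shown. Sustained abstinence is captured directly by the three abstinence measures.

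**The case for a change.** The case for a split is reasonable. The protocol itself says recent quitters are in the population. The Enrollment section allows 14 days between screening and completing baseline, so someone smoking at screening may be abstinent by then. An unknown share is a reason to count it, and the count costs almost nothing. The mechanism can also be hidden: at an assumed share of 20%, raising initiation from 15% to 25% with maintenance at 50% gives 22% against 30%, and raising maintenance from 50% to 90% with initiation at 15% gives the same pair.

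What stands is that the gap is real and that a count of entry status would help a reader. The rest weakens at a plausible share. Nothing in the documents supports 20%. At 5%, the same rise in maintenance moves the overall rate by 0.05 × 0.40 = 2.0 points, while the same rise in initiation moves it by 0.95 × 0.10 = 9.5 points, so the two are no longer interchangeable.

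The plan's silence is also general. Apart from recruitment source it specifies no baseline table for any variable, so the missing row reflects brevity and not a decision to leave entry status out.

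**Conclusion.** The observation is correct, but the plan needs no change. It states who is eligible and reports abstinence in the people it enrolls, which is a coherent target for an exploratory pilot. The fourth aim promises a comparison of cessation outcomes between the apps; it does not promise a rate of new quitting among current smokers.

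At a share of 2-5%, the quit rate is raised by an assumed 0.4 to 3.5 points, and the comparison of arms carries no systematic bias. This rests on the share being small, which the text suggests but does not state, and on the assumed abstinence rates. At 10% the rise would be 2 to 7 points, and a sentence of interpretation in the report would then matter more. Analysts can meet that need by describing entry status from the baseline Tobacco Use items, if those items establish it. That is an ordinary reporting choice and leaves every planned analysis as it is.
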